7.2.2. RT planning

A three-dimensional conformal RT (3D-CRT) with photons $\geq 6\text{MV}$ will be realized based on the acquisition of a CT-scan performed in treatment position. Intensity modulated RT (IMRT), volumetric modulated arctherapy (VMAT) and tomotherapy are authorized.

Treatment position will be defined according to the location of the tumor and personalized contention could be used. Surgical scar, drain orifices or biopsy path could be spotting with radio opaque markers.

7.2.3. Volume definition

The definition of volumes will be in accordance with ICRU (International Commission of radiotherapy Unit) reports #50, #62 and #83.

Targets volume need to be define as report in Haas et al. report (International Journal of Radiation Oncology, Biology and Physics 2012)

- The GTV (Gross Tumor Volume) will be defined on CT, ideally after fusion with MRI (axial T1 contrast-enhanced sequence).
- The CTV (Clinical Tumor Volume) will be defined by adjunction of a 4 cm margin around the GTV, in the longitudinal directions and 1.5 cm in others directions. This margin could be shortened according to anatomical barriers as bone, interosseous membranes or fascial planes. Margin could be extended too in order to include an entire anatomical compartment or identified peri-tumoral oedema. The CTV will have to include surgical scar or biopsy paths.
- The PTV (Planning Target Volume) will be defined by adjunction of a set-up margin around the CTV to take into account patient set-up uncertainties. This margin will have to be selected by each participating center depending on their equipment, irradiation techniques and experiences.
- The OAR (Organs At Risk) as bone, neurovascular axis, muscular compartments, spinal cord, brachial plexus will be defined according to the location of the tumor (Cancer Radiotherapy, vol 14, 2010, special issue).

7.2.4. Dose prescription, specification and reporting in the PTV

Dose prescription, specification and reporting will be done according to ICRU report 83 recommandations.

During DOSE ESCALATION PHASE:

The prescribed dose at the median of the PTV (for IMRT treatments) or at the ICRU point (for non-IMRT treatments) will be 59.4Gy in 33 fractions of 1.8Gy, with 5 fractions per week.

During EXPANSION PHASE: Total radiotherapy dose will be adapted with patient condition (operable patient/inoperable patient):

- Up to 50 Gy for resectable disease or potentially resectable disease after study treatment (in 25 fractions of 2 Gy, with 5 fractions per week)
- Up to 59.4 Gy for unresectable disease (in 33 fractions of 1.8Gy, with 5 fractions per week).

95% of the PTV will have to receive at least 95% of the prescribed dose. Dose homogeneity inside the PTV will have to be comprised between 95% and 107% of the prescribed dose. The maximal dose should not exceed 107% of the prescribed dose.

7.2.5. Adverse effects management

Acute toxicities of radiotherapy of STS are essentially musculoskeletal or cutaneous toxicities. They will be evaluated through a clinical examination performed each week during radiotherapy and one month after the end of radiotherapy (D8, D15, D22, D29, D36, D43, D50, D64, D78, D92) or until regression of a grade 3. Grading of adverse events will be done according to the CTCAE v.4.

- If a grade ≥ 3 musculoskeletal or cutaneous toxicity is observed before a radiotherapy dose of 30Gy, Olaparib and radiotherapy were stopped (DLT) but radiotherapy could be continued when regression to a grade ≤ 2 will be achieved.
- If a grade ≥ 3 musculoskeletal or cutaneous toxicity is observed after a radiotherapy dose of 30Gy, radiotherapy will be stopped until regression to a grade ≤ 2 and then will be continued. Olaparib will be continued during radiotherapy interruption. If grade ≥ 3 persits more than 4 weeks, Olaparib will be stopped (DLT).

The irradiated skin area that will be included in the operative volume must be identified during contouring and protected during planification (ALARA) in order to limit the occurrence of post-operative acute cutaneous and mucous complications [30 - 31].

7.3.ASSOCIATED TREATMENT: SURGERY FOR RESECTABLE DISEASE

Surgery will be performed by expert surgeon within 12 weeks of radiotherapy completion in reference centers labelled by the French NCI and NETSARC network.

Post-operative complications will be recorded up to 12 months after surgical complication.

Surgical sample will be analyzed to determine histological response and data will be collected in case report form.

The decision of surgery has to be taken by the investigational site during Multidisciplinary Tumor Board (RCP),

The decision of surgery has to be notified to the sponsor as soon as possible (i.e. before surgery).

Post-surgery clinical exam: addition of 3 visits after surgery (D30, D60 and D90). The next visits remain unchanged (follow-up every 3 months).

Post-surgery complications grade 3 should be reported immediately as serious adverse event to the Vigilance Unit of the Sponsor.

CONFIDENTIAL

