
	
13. Patients with myelodysplastic syndrome/acute myeloid leukaemia,
 
14. Major surgery within 14 days of starting study treatment,
 
15. Participation to a study involving a medical or therapeutic intervention in the last 30 days,
 
16. Patient unable to follow and comply with the study procedures because of any geographical, familial, social or psychological reasons,
 
17. Previous enrollment in the present study,
 
18. Patients with a known hypersensitivity to olaparib or any of the excipients of the product,
 
19. Patients who not have recovered from any effects of any major surgery,
 
20. Individuals deprived of liberty or placed under legal guardianship.
 
21. Patients who have tumor in contact with, invading or encasing for more than 50% any major blood vessels and/or patients requiring vascular reconstruction.
																												
Route of administration	
Olaparib will be administered per os bi-daily, as appropriate assigned dose level, during 7.5 weeks (D1 to D52). Olaparib should be started one week before the start of radiotherapy and will be continued until the last day of radiotherapy. Beyond this period, Olaparib could be continued at the investigator’s discretion and after sponsor authorization, until progression.
 
Radiotherapy consists of fractionated focal irradiation: During Dose escalation: At a dose of 1.8 Grays (Gy) per fraction given once daily five days per week (Monday through Friday) over a period of 6.5 weeks, for a total dose of 59.4 Gy. Radiotherapy starts at D8.
 
During expansion cohort: Resecable tumors: At a dose of 2 Grays (Gy) per fraction given once daily five days per week (Monday through Friday) over a period of 5 weeks, for a total dose up to 50 Gy. Radiotherapy starts at D8. Unresecable tumors: At a dose of 1.8 Grays (Gy) per fraction given once daily five days per week (Monday through Friday) over a period of 6.5 weeks, for a total dose of 59.4 Gy. Radiotherapy starts at D8.
																												

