 - Stopping rule: inclusions will stop in the dose escalation trial after 24 eligible and assessable patients enrolled.
- For the dose escalation part, a DLT validation committee will be consulted before the first escalation to a new dose level (see section 12.1.2).
- Conclusions of the steering committee for the MTD definition will be submitted to an independent committee (IDMC) before opening the expansion cohort.

3.5.EXPANSION COHORT

- Once the MTD and the RP2D have been defined based on the dose escalation study, the expansion cohort will be opened. All patients will be treated at the RP2D of Olaparib (as defined in the escalation trial) given in association with concomitant radiotherapy at a dose that depends on tumor status:
 - Resectable tumor or potentially resectable tumor after study treatment: up to 50 Gy
 - Unresectable tumor: up to 59.4 Gy.
- Following the expansion cohort, the **RP2D for Olaparib** may be refined by the steering committee based on the MTD and RP2D (as defined at the end of the dose escalation trial), as well as additional safety data including safety data from the expansion cohort, PK and PD data. Data from all patients (escalation + expansion) will be used to refine the RP2D.

3.6.PATIENT'S REPLACEMENT

See section 10.2

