4. SELECTION OF PATIENTS

4.1. INCLUSION CRITERIA

1. Histology: patients with soft-tissue sarcoma histologically confirmed by central review (Pr [name] team), except if the diagnosis was already confirmed by the RRePS Network,
2. Upper/Lower limb or trunk wall soft-tissue sarcoma,
3. Age ≥ 18 years,
4. Locally advanced or locally recurrent primitive tumor, outside any previously irradiated field. Patients presenting operable locally advanced or locally recurrent tumor can be included. Patients with metastases can be included in the protocol,
5. Eastern Cooperative Oncology Group (ECOG), performance status ≤ 2 ,
6. Life expectancy ≥ 6 months,
7. At least one lesion, not previously irradiated, that can be accurately measured at baseline as ≥ 10 mm in the longest diameter (except lymph nodes which must have short axis ≥ 15 mm) with magnetic resonance imaging (MRI) and which is suitable for accurate repeated measurements,
8. Adequate hematological, renal, metabolic and hepatic function:
 - Haemoglobin ≥ 9 g/dL and no blood transfusions in the 14 days prior to study entry
 - Absolute neutrophil count (ANC) $\geq 1.5 \times 10^9/L$
 - Platelets $\geq 100 \times 10^9/L$
 - Total bilirubin $\leq 1.5 \times$ upper limit of normality (ULN),
 - Alanine aminotransferase (ALAT) or aspartate aminotransferase (ASAT) $\leq 2.5 \times$ ULN,
 - Serum creatinine $\leq 150 \mu\text{mol/L}$ or creatinine clearance $\geq 50 \text{ mL/min}$ (according to local institution) in case of serum creatinine $> 150 \mu\text{mol/L}$,
 - TP, INR $\leq 1.5 \times$ ULN
9. Women of childbearing potential must have a negative serum pregnancy test within 28 days of study treatment, confirmed prior to treatment on day 1. Female patients of child bearing potential and their partners, who are sexually active, must agree to the use of two highly effective forms of contraception in combination throughout the period of taking study treatment and for at least 1 month after last dose of study drug. Males patients, who are sexually active, and their partners of child bearing potential must agree to the use of two highly effective forms of contraception in combination throughout the period of taking study treatment and for at least 3 month after last dose of study drug. Acceptable birth control methods are described in appendix 6. Subjects of non-childbearing potential are those who have:
 - Amenorrheic for 1 year or more following cessation of exogenous hormonal treatments,

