8.2.2. Centralized Radiological Review (Institut Bergonié)

8.2.2.1. GENERAL PROCEDURE

Centralized radiological review will be performed to confirm disease status at 6 months in comparison with baseline, Week#12 and Week#24 and every 8 weeks for patients with metastatic disease at inclusion. For patients included in the reference center, MRI and CT scan (for patients with metastatic disease) will be initially read by a radiologist who differs from the expert.

Review process will be centralized at Institut Bergonié and will be performed by a radiologist expert in

soft tissue sarcomas.

In case of discordance between the local radiologist and the expert reviewer, the judgment provided by the expert reviewer will be retained and used in statistical analyses.

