Conventional CT and MRI: This guideline has defined measurability of lesions on CT scan based on the assumption that CT slice thickness is 5 mm or less. If CT scans have slice thickness greater than 5 mm, the minimum size for a measurable lesion should be twice the slice thickness. MRI is also acceptable in certain situations (e.g. for body scans).

RESPONSE CRITERIA

Evaluation of Target Lesions

Complete Response (CR): Disappearance of all target lesions. Any pathological lymph nodes (whether target or non-target) must have reduction in short axis to <10 mm.

Partial Response (PR): At least a 30% decrease in the sum of the diameters of target lesions, taking as reference the baseline sum diameters.

Progressive Disease (PD): At least a 20% increase in the sum of the diameters of target lesions, taking as reference the smallest sum on study (this includes the baseline sum if that is the smallest on study). In addition to the relative increase of 20%, the sum must also demonstrate an absolute increase of at least 5 mm. (Note: the appearance of one or more new lesions is also considered progressions).

Stable Disease (SD): Neither sufficient shrinkage to qualify for PR nor sufficient increase to qualify for PD, taking as reference the smallest sum diameters while on study

Evaluation of Non-Target Lesions

Complete Response (CR): Disappearance of all non-target lesions and normalization of tumor marker level. All lymph nodes must be non-pathological in size (<10 mm short axis)

Note: If tumor markers are initially above the upper normal limit, they must normalize for a patient to be considered in complete clinical response.

Non-CR/Non-PD: Persistence of one or more non-target lesion(s) and/or maintenance of tumor marker level above the normal limits

Progressive Disease (PD): Appearance of one or more new lesions and/or unequivocal progression of existing non-target lesions.

Although a clear progression of "non-target" lesions only is exceptional, the opinion of the treating physician should prevail in such circumstances, and the progression status should be confirmed at a later time by the review panel (or Principal Investigator).

Definition of the Best Response

The best response determination in trial where confirmation of complete or partial response is required:

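### Neither document says how a resected tumour is scored, so surgery before the week-24 MRI can count as 6-month non-progression on olaparib plus radiotherapy

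*Protocol*

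**What the plan says.** - **Who enters.** Protocol 4.1, criterion 4: "Patients presenting operable locally advanced or locally recurrent tumor can be included". Patients with metastases may also enter.
- **Radiotherapy in the expansion cohort.** Section 3.5: "Resectable tumor or potentially resectable tumor after study treatment: up to 50 Gy". Section 7.2.4 gives this as "in 25 fractions of 2 Gy, with 5 fractions per week"; unresectable tumours get 33 fractions. The synopsis adds "Radiotherapy starts at D8".
- **Surgery.** Section 7.3: "Surgery will be performed by expert surgeon within 12 weeks of radiotherapy completion". The site's tumour board decides. No earliest date is given. Histological response is to be recorded.
- **Imaging and endpoint.** MRI is at weeks 12 and 24, within 7 days (5.5). Section 8.2.2.1: "Centralized radiological review will be performed to confirm disease status at 6 months in comparison with baseline, Week#12 and Week#24". The primary endpoint is CR, PR or SD at 6 months by RECIST 1.1 (9.2 and synopsis).
- **Scoring.** Appendix 3: "Complete Response (CR): Disappearance of all target lesions". It makes no exception for a lesion removed by a surgeon. SAP 3.2.1.2 counts any assessment at 6 or later with an overall response of CR, PR or SD, and uses no surgery variable.
- **Go rule.** Section 10.1 requires 14 assessable patients. At least one non-progression observed under treatment makes the combination worth further testing.
- **SAP population.** The SAP synopsis and SAP 2.2.1 still require an inoperable tumour.

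**The concern.** The expansion cohort is meant to show preliminary activity of olaparib given with radiotherapy. A patient whose only target lesion has been excised has nothing left to measure at week 24. Unless disease has appeared elsewhere, the written definitions return a success whatever the drug and radiotherapy did. With a go rule of 1 in 14, very few such patients could decide the outcome. The pooled rate would also mix two groups with different radiotherapy courses and different local treatment, and no planned analysis separates them.

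**Working it through.** **1. The plan's own sample size.** Gehan's first stage takes the smallest n with (1 − 0.20)^n ≤ 0.05. 0.8^13 = 0.055 and 0.8^14 = 0.044, so n = 14, as stated.

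**2. Timing.** Fractions are counted Monday to Friday from day 8. The 33-fraction count gives day 52, which agrees with the synopsis. Twelve weeks are 84 days. In the schedule of assessments week 12 is day 78 = 7 × 11 + 1, so week 24 is day 7 × 23 + 1 = 162, with a window of days 155 to 169.

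| Course | Radiotherapy ends | Latest surgery | Days before window opens |
|---|---|---|---|
| 25 fractions | D40 | 40 + 84 = D124 | 155 − 124 = 31 |
| 33 fractions, if surgery follows | D52 | 52 + 84 = D136 | 155 − 136 = 19 |

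A 28-day radiotherapy interruption moves the limits to D152 and D164. Of these, only the interrupted 33-fraction course reaches the window. With no earliest date for surgery, even the week-12 MRI (day 78) could be post-operative.

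**3. Scoring under the written rules.**
- Sole target lesion removed, no new lesion: the sum of diameters is zero, so CR, which is non-progression.
- Primary removed, metastatic target lesions remain: PR, SD or PD, depending on those lesions.
- Protocol 9.1 asks for CR and PR to be confirmed at least 4 weeks later. SD carries no such requirement, and the expansion derivation in SAP 3.2.1.2 omits the check.
- Protocol 10.2 lists surgery neither as a failure nor as an exclusion. A week-12 scan meets its requirement of a measurement at 8 weeks or later, so resected patients stay in the denominator.

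**4. Size.** The resected share is assumed.
- Let k of 14 be resected, unrelapsed and scored as successes. The 6-month non-progression rate is then at least k/14: 3/14 = 21%, 5/14 = 36%, 7/14 = 50%.
- Let each patient have probability f of being resected and scored a success, with true non-progression of 0% in all others. The chance of a go is 1 − (1 − f)^14: 77% at f = 10%, 96% at 20%, 99.3% at 30%.

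**5. Time point of the go rule.** For a 25-fraction course without continued olaparib, the on-treatment period in section 5.2 ends about day 40 + 42 = 82, well before week 24. Section 10.1 (under treatment) and the 6-month endpoint therefore describe different times.

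**The case against.** A reader might infer that every resectable patient is operated on, and that each unrelapsed one must be scored as a 6-month responder. The documents do not go that far. Surgery is a tumour-board decision. No passage says that a resected lesion is a CR, and the central reader could record it as not evaluable. With residual metastases, removing the primary may shrink the sum of diameters by less than 30%, which is SD, and other lesions may progress. The floor on the objective response rate is therefore at or below the non-progression floor. These points stand. Leaving the choice to the central reader is still an unplanned decision on the primary endpoint.

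The go rule's own wording may also exclude a week-24 scan. That stands as a contradiction to be resolved. It is not a safeguard, because the primary analysis uses 6-month status.

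It is also tempting to drop resected patients from the primary analysis. Section 7.3 calls surgery an associated treatment, and sections 5.6 and 11.5 distinguish it from a new anti-tumour therapy, so non-progression under the whole strategy is a defensible quantity. Section 3.5 includes tumours that become resectable after study treatment. Dropping those patients would select on a post-baseline event, possibly removing those who did best, and would exceed Gehan's 5% limit from the first exclusion.

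Finally, the analyses are descriptive. The go rule is still a decision rule and would be applied to these data.

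**Conclusion.** The concern holds as a missing rule with a predictable direction. For uninterrupted courses, surgery within the protocol's window always precedes the week-24 MRI, by at least 31 days (25 fractions) or 19 days (33 fractions) from the opening of the scan window. Applied literally, the definitions credit removal of a sole target lesion to olaparib plus radiotherapy. The floors of 21%, 36% and 50% rest on assumed counts of 3, 5 and 7 of 14, all unrelapsed and all scored as successes; the true share is unknown. One such patient could meet the go rule if it is read on the 6-month endpoint. The documents do not show that all resectable patients will be resected, that all will be scored CR, or that they should leave the primary analysis.

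**What to change.** Amend protocol 9.2 and 10.1, and SAP 3.2.1.2 and 3.2.2:

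1. Score RECIST objective response only from scans before surgery. Use post-operative imaging only to detect relapse or new lesions. Patients with no post-baseline pre-operative scan are not evaluable for response, stay in the denominator and are listed.
2. Report 6-month non-progression for all assessable patients, and separately for resected patients (pre-operative response, histological response, relapse by week 24) and unresected patients. State that the all-patient rate reflects olaparib plus radiotherapy with surgery where performed.
3. State that disappearance of a lesion through resection cannot by itself satisfy the go rule, and align the rule's time point with the 6-month endpoint.
4. Update the SAP, which still assumes inoperable tumours, and add a surgery date to the endpoint derivation.

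**Cost.** This needs wording and a few table columns. Histological response is already collected, but no MRI is tied to surgery, so some patients may lack a pre-operative scan.

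The statistical price should be stated. If k of 14 are resected and contribute no success, the chance of seeing none at a true 20% rate is 0.8^(14 − k): 0.8^13 = 5.5% for k = 1, 0.8^9 = 13% for k = 5 and 0.8^7 = 21% for k = 7, against 4.4% planned. Keeping 14 unresected patients would take 14/(1 − f) assessable patients: 16, 18, 20 or 28 at f = 10%, 20%, 30% or 50%, where f is here the share resected.

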8. STUDY EVALUATIONS

Study evaluations aim to assess:

- Diagnosis
- Efficacy
- Safety

8.1.CENTRAL REVIEW FOR DIAGNOSIS OF SARCOMA

8.1.1. Diagnosis of sarcoma

If diagnosis of sarcoma was not confirmed by the RRePS Network, pathological central review will be performed to confirm histological diagnosis of sarcoma by Pr. [name] and collaborators, Department of Pathology, Institut Bergonié, Bordeaux, France. The reviewer will assess pathological diagnosis; document the results on the 'Pathological request form' response completed and sign this form.

Every discrepancy will be discussed between referral investigator, Pr [name] or collaborators and the Sponsor, until a final decision is reached. Patients with diagnosis different from sarcoma will be considered ineligible and will not be included in the study.

8.1.2. Pathological specimen sampling necessary for central review

For a gross description and diagnostic information concerning pathological specimens, reference to "Recommendations for reporting soft tissue sarcomas" is strongly advised (Recommendations, 1999). Available tumor samples obtained at diagnosis or at relapse, as unstained slides (10), and/or preferable paraffin-embedded tumor blocks (one or two) are mandatory for central review.

8.1.3. Pathological process schedule and implementation (not applicable if diagnosis reviewed in RRePS Network)

Each site will send to Institut Bergonié within 7 days after the signature of informed consent:

- Pathology request form completed
- 10 unstained slides and/or preferable FFPE (Formalin-Fixed Paraffin-Embedded) block of specimen tumor sampling, obtained anytime during disease development
- Initial pathology report with patient code and date of birth (including macroscopic description) and pathology report of molecular biology if any.

All material must be sent as described in a specific SOP provided by the Sponsor.

8.2.EFFICACY ONLY FOR EXPANSION COHORT

The antitumor activity of Olaparib given in association with radiotherapy will be evaluated in terms of Objective response under treatment, 6-months Objective response rate (ORR), 6-months Non-progression rate (NPR), 1-year Progression-free survival (PFS), 1-year Overall survival (OS). Non-progression rate and best objective response are defined as per the Response Evaluation Criteria in Solid Tumors (RECIST v1.1).

